5.3 Duration of follow-up

Patients will be followed for 4 weeks after removal from study and patient records will be reviewed until death or 2 years from enrollment (whichever comes first) to assess progression and survival. Patients removed from study for unacceptable adverse event(s) will be followed until resolution or stabilization of the adverse event.

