6.5 Schedule of events

Experimental arm

Assessment	Screening + First visit	Week 5 ^a	Week 9 ^a	Week 17 ^a	Week 21 ^a
Signed informed consent	X				
Vital signs	X				
CBC/d/p ^d	X				
CRP, Serum IG's, LDH	X				
Myeloma proteins ^e	X				X
Blood for research ^f	40 mL	40 mL			40 mL
Fluzone HD	X		X	X	
Prevnar (PCV13)		X			
Record grade \geq 2 adverse events ^g	X		X	X	
Influenza-like illness update ^b		X	X	X	X
PFS and OS ^h					X

Control arm

Assessment	Screening + First Visit	Week 5 ^a	Week 9 ^a	Week 17 ^a	Week 21 ^a
Signed informed consent	X				
Vital signs	X				
CBC/d/p ^d	X				
CRP, Serum IG's, LDH	X				
Myeloma proteins ^e	X				X
Blood for research ^f	40 mL	40 mL			40 mL
Fluzone HD	X				
Prevnar (PCV13)		X			
Record grade \geq 2 adverse events ^g	X				
Influenza-like illness update ^b		X	X	X	X
PFS and OS ^h					X

- a. Assessments on these days can be performed within a \pm 5 day window. Subsequent visits (weeks 5, 9, 17, 21) are based on the actual time of Fluzone HD vaccination, not the pneumonia vaccination.
- b. Involves contact between study personnel and the patient regarding influenza-like illness and SAEs. An in-person visit is not required.
- c. All patients (N=148) will have research blood drawn for correlative science. In both arms, blood will be obtained at baseline, week 5, and week 21. The first 20 patients in each group (n=40 total), split evenly between intervention arm (20 experimental, 20 control), had additional blood drawn 1 week after each Fluzone HD dose (week 2 for control arm and weeks 2, 10, and 18 in the experimental arm) – this was completed 17-Nov-2019.
- d. CBC, differential, and platelets will be performed pre-vaccination.
- e. If not done with results available within 30 days of initial vaccination, a modified myeloma disease assessment requested but not required to include SPEP and free light chains if either were measurable per IMWG criteria in the past. Serum IgD or IgE are requested if a monoclonal IgD or IgE were present in the past. For patients with an IgA monoclonal protein, Hevylite IgA can be used to replace serum immunoglobulins and SPEP.
- f. Peripheral blood samples will be obtained and analyzed as described in correlative science section.

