9. RESPONSE

Time to progression (TTP): Time to progression is defined as the time from last treatment until progression. Patients who have died without evidence of progression are censored in the TTP analysis at the time of death and patients who are alive without progression are censored at the last disease assessment.

Progression-Free Survival (PFS): Defined as the time from last treatment to the disease progression or death from any cause. Patients who have not progressed or died are censored at the date last known progression-free. Patients with no on-study assessment will be censored at the time of registration.

Overall survival (OS): OS is defined as the time from randomization to death. Alive patients are censored at the date last known alive.

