10.3 Sample size determination

In the initial design, the sample sizes of 81 in each group achieved 90% power to detect a difference between the group proportions of 0.2520. The proportion in group one (the intense Fluzone HD arm) is assumed to be 0.3330 under the null hypothesis and 0.5850 under the alternative hypothesis. The proportion in group two (the control group) is 0.3330. The test statistic used is the two-sided Z test with pooled variance. The significance level of the test (the alpha) was targeted at 0.0500, i.e. the probability of rejecting a true null hypothesis that was desired. The significance level

actually achieved by this design is 0.0513. The planned power was 0.9, i.e. the probability of rejecting a false null hypothesis. We assume 10% drop off rate in the study so that we planned to enroll 90 patients in each group.

During the first influenza season (2019-2020), we enrolled 50 patients of which only 23 were evaluable as 27 patients missed the week 21 study assessment due to COVID19.

We aim to complete the trial during the influenza season 2020-2021, and hence will need to control season as a confounder through a logistic regression model. A logistic regression of a binary response variable (e.g. HAI>40) on a binary independent variable (e.g. the treatment arms) with a sample size of 134 observations (of which the two treatment arms are evenly distributed) achieves 80% power at a 0.05 significance level to detect a change in the rate of HAI>40 from the baseline value of 0.333 to 0.585. This change corresponds to an odds ratio of 2.82. An adjustment was made since a multiple regression of the independent variable of interest on the other independent variables (e.g. the seasons) in the logistic regression obtained an R-Squared of 0.1. Hence we will need 67 patients in each randomized arm. After taking into account the expected 10% dropout rate, we plan to enroll 74 patients in each arm, producing a total sample size of 148 patients. Given we already accrued 11 evaluable patients per arm during the first season, we will plan to enroll an additional 125 patients in the second season.

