10.4.6 Analysis of secondary endpoints

Time to event outcomes including TTP, PFS and OS will be assessed with patients censored at time of last follow-up. TTP, PFS and OS rates of two patient groups will be estimated with the Kaplan-Meier method and compared between different groups using the log-rank test, respectively. The TTP, PFS and OS of each patient group at specific time points, such as 1 year, 3 years, and 5 years, etc. will be estimated alone with 95% CI. Cox proportional hazards models will be used in the multivariable analyses to assess adjusted effects of biomarkers on the patients' TTP, PFS and OS after adjusting for other factors. The proportional hazards assumption will be evaluated graphically and analytically with regression diagnostics.

Protocol therapy related toxicities rate will be summarized using descriptive statistics such as frequencies and proportions. Differences in the proportion of patients who experience protocol-related toxicities will not be compared between cohorts.

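### PFS is censored at registration for patients without an on-study assessment, which gives zero or negative time and conflicts with Sections 10.4.6 and 5.3

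*Combined protocol and SAP*

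**What the plan says.** All references are to the combined protocol and SAP.

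- **Section 9, PFS definition:** "Defined as the time from last treatment to the disease progression or death from any cause".
- **Section 9, PFS censoring, general rule:** "Patients who have not progressed or died are censored at the date last known progression-free".
- **Section 9, PFS censoring, next sentence:** "Patients with no on-study assessment will be censored at the time of registration". The term *on-study assessment* is not defined anywhere, and no exception is written for a death or for progression found in the chart.
- **Section 10.4.6:** "Time to event outcomes including TTP, PFS and OS will be assessed with patients censored at time of last follow-up".
- **Section 5.3:** "patient records will be reviewed until death or 2 years from enrollment (whichever comes first) to assess progression and survival".
- **Section 6.5:** the row "Myeloma proteins" is marked at the first visit and at week 21 only, in both arms. The PFS and OS row is marked at week 21 only. Footnote h says survival data come from the chart without a visit.
- **Section 6.5, footnote e, attached to the myeloma row:** "a modified myeloma disease assessment requested but not required to include SPEP and free light chains". The footnote opens with a condition about results near the first vaccination.
- **Section 10.3, first season:** of 50 enrolled, "only 23 were evaluable as 27 patients missed the week 21 study assessment due to COVID19".

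**The concern.** A registration-censoring rule suits a trial with frequent mandatory disease assessments, where a patient with none really has no follow-up. Here only one myeloma test is scheduled after baseline, and progression and survival are to be read from the chart for up to 2 years. A patient can therefore have no study assessment and still have a well-documented course. Read literally, the sentence discards that information.

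It also places the censoring date before the PFS clock starts for anyone whose last dose came after week 1. Section 9 and Section 10.4.6 then give the analyst two different censoring dates for the same patient, with no order of precedence.

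PFS feeds the log-rank comparison of the arms, the time-point rates and the biomarker Cox models in Section 10.4.6, and the analysis of peak HAI against PFS in Section 10.4.5.

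**Working it through.** The plan gives no sample size, event count or power for PFS, so there is no stated PFS figure to reproduce. The check is on the times that the rule produces and on how the rules fit together.

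**1. Time assigned by the registration rule**

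Inputs: registration in week 1, with consent and eligibility (schema); last Fluzone HD dose at week 17 (experimental) or week 1 (control), from Section 6.5; PFS origin at last treatment (Section 9). I take last treatment to mean the last Fluzone HD dose.

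Formula: PFS time = week of registration − week of last dose.

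- Control: 1 − 1 = 0 weeks.
- Experimental, all three doses: 1 − 17 = −16 weeks (−16 × 7 = −112 days).
- Experimental, stopped after the second dose (week 9): 1 − 9 = −8 weeks (−56 days).

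The ±5-day visit window does not change the sign of either negative figure. Moving the origin to randomization would bring the times to about zero, but the follow-up would still be lost.

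**2. Time the same patient has in the chart**

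Take 2 years as 104 weeks from enrollment, with no event.

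- Control: 104 − 0 = 104 weeks.
- Experimental, all three doses: 104 − 16 = 88 weeks.

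**3. The rules side by side, for a patient with no on-study assessment**

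| Chart shows | Registration sentence, read literally | Other PFS sentences in Section 9 | Section 10.4.6 |
|---|---|---|---|
| Event-free to 2 years | Censored at 0 or −16 weeks | Censored when last known progression-free | Censored at last follow-up, 104 or 88 weeks |
| Progression | Censored at 0 or −16 weeks | Event | No separate event rule |
| Death without progression | Not settled by the text | Event | No separate event rule |

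TTP, defined in the same section and also timed from last treatment, has no registration rule. A patient with progression only in the chart would be a TTP event and yet, on the literal reading, censored for PFS.

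**4. How many patients**

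The documents do not give this number. The only related figure is for the first season: 50 − 23 = 27 missed the week-21 study assessment, and 27/50 = 54%.

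- If a baseline test or chart-reviewed results count as an assessment, the share affected is near zero.
- If only the week-21 study visit counts, the first-season share would be up to 54%.
- Section 10.3 treats those 27 as not evaluable, and the plan does not say whether they enter the PFS analysis.

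**The case against.** Much of the case on the other side stands.

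- **Deaths.** A reader might infer that patients who die without an assessment are dropped as events. The text does not establish this. Section 9 first makes any death an event, and the sentence just before the disputed one is limited to event-free patients. The disputed sentence can naturally be read as the fallback for that same group. What stands is that the plan does not say so.
- **An optional week-21 test.** A reader might infer from footnote e that the week-21 test is optional. The footnote marks the whole row, but its opening condition concerns the first vaccination, and the schema lists the week-21 myeloma proteins as standard of care. The point does not need this inference: one scheduled test and an undefined term are enough.
- **A share of about 23%.** A reader might add the 27 first-season patients to a 10% loss among 125 second-season patients: 27 + 12.5 = 39.5, and 39.5/175 = 22.6%. The documents do not support this as an estimate. The 27 missed a study assessment, and nothing shows that they lacked clinic myeloma tests or chart follow-up. The 10% is a sample-size allowance for dropout.
- **Informative censoring.** The only documented reason for the missed visits is the pandemic, so censoring related to prognosis is possible but not shown.
- **The competing rule.** Under Section 10.4.6 these patients would contribute time. That makes the defect an unresolved contradiction rather than a certain loss of data; it does not remove the contradiction.
- **Importance.** PFS is not among the objectives or endpoints in Sections 1 and 2.

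**Conclusion.** The rule is wrong as written. On a clock that starts at the last Fluzone HD dose it gives 0 weeks in the control arm and −16 weeks in a fully dosed experimental-arm patient, where the chart could hold up to 104 and 88 weeks. It contradicts the censoring rule in Section 10.4.6 and does not fit the 2-year record review in Section 5.3. It turns on an undefined term and leaves the handling of deaths without an assessment unstated.

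The times rest on two assumptions: registration falls in week 1, and last treatment means the last Fluzone HD dose. The number of patients affected cannot be derived from the documents and could be near zero. The effect is confined to PFS and the analyses that use it. The primary week-21 HAI endpoint is unaffected, and so is OS, which has its own origin and censoring rule.

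**What to change.** 1. In Section 9, delete the registration-censoring sentence. Alternatively, limit it to patients with no information of any kind after registration, and give them zero time at the PFS origin.
2. In Section 9, state that progression or death found in the 2-year record review is a PFS event whether or not study visits took place.
3. State that event-free patients are censored at the date they were last known to be progression-free in that review.
4. Make Section 10.4.6 give the same PFS rule as Section 9. If *on-study assessment* is kept anywhere, define it and say whether baseline and clinic results count.
5. In Section 6.5, mark the PFS and OS row as record review to 2 years for both progression and survival.

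The cost is protocol and SAP wording only. The record review is already planned, so no visits, samples or patients are added.

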10. STATISTICAL CONSIDERATIONS

10.1 Statistical hypotheses

This is a randomized study to determine whether three doses of Fluzone HD, aka continuous dosing throughout the influenza season will maintain seroprotection throughout the entire study. Specifically we hypothesize that 58% of patients in the experimental arm will achieve seroprotection at week 21, e.g. HAI >40 ; the null hypothesis is that only 33% will demonstrate seroprotection at the end of the study.

10.2 Analysis datasets

Safety Population: The safety analysis dataset will include all eligible patients who begin treatment and receive at least one dose of protocol therapy. Patients will be analyzed in the cohort to which they were enrolled.

Efficacy Evaluable Population: All evaluable patients will be included in the analysis of efficacy endpoint. The term evaluable is defined as any eligible patient who receives at least one dose of protocol therapy and does not withdraw consent until the patient's first response assessment. Patients who fail to have a response assessment due to early progression or death will be categorized as non-responders.

10.3 Sample size determination

In the initial design, the sample sizes of 81 in each group achieved 90% power to detect a difference between the group proportions of 0.2520. The proportion in group one (the intense Fluzone HD arm) is assumed to be 0.3330 under the null hypothesis and 0.5850 under the alternative hypothesis. The proportion in group two (the control group) is 0.3330. The test statistic used is the two-sided Z test with pooled variance. The significance level of the test (the alpha) was targeted at 0.0500, i.e. the probability of rejecting a true null hypothesis that was desired. The significance level

actually achieved by this design is 0.0513. The planned power was 0.9, i.e. the probability of rejecting a false null hypothesis. We assume 10% drop off rate in the study so that we planned to enroll 90 patients in each group.

During the first influenza season (2019-2020), we enrolled 50 patients of which only 23 were evaluable as 27 patients missed the week 21 study assessment due to COVID19.

We aim to complete the trial during the influenza season 2020-2021, and hence will need to control season as a confounder through a logistic regression model. A logistic regression of a binary response variable (e.g. HAI>40) on a binary independent variable (e.g. the treatment arms) with a sample size of 134 observations (of which the two treatment arms are evenly distributed) achieves 80% power at a 0.05 significance level to detect a change in the rate of HAI>40 from the baseline value of 0.333 to 0.585. This change corresponds to an odds ratio of 2.82. An adjustment was made since a multiple regression of the independent variable of interest on the other independent variables (e.g. the seasons) in the logistic regression obtained an R-Squared of 0.1. Hence we will need 67 patients in each randomized arm. After taking into account the expected 10% dropout rate, we plan to enroll 74 patients in each arm, producing a total sample size of 148 patients. Given we already accrued 11 evaluable patients per arm during the first season, we will plan to enroll an additional 125 patients in the second season.

10.4 Statistical methods

10.4.1 Design operating characteristics

N/A

10.4.2 Safety analyses

Adverse event data will be described and graded per the NCI CTCAE guidelines. For each adverse event, information to be collected includes event description, time of onset, clinician assessment of severity, relationship to study product (assessed only by those with the training and authority to make a diagnosis), and time of resolution/stabilization of the event. All vaccine-related AEs will be recorded with start dates occurring any time after patient receives any study drug until 7 (for non-serious AEs) or 100 days (for SAEs) after the last day of study participation. At each study visit, the investigator will inquire about the occurrence of AE/SAEs since the last visit. Events will be followed for outcome information until resolution or stabilization.

Any medical condition that is present at the time that the participant is screened will be considered as baseline and not reported as an AE. However, if the study participant's condition deteriorates at any time during the study, it will be recorded as an AE. Changes in the severity of an AE will be documented to allow an assessment of the duration of the event at each level

of severity to be performed. AEs characterized as intermittent require documentation of onset and duration of each episode.

The maximum grade for each type of toxicity will be recorded for each patient, and frequency tables will be reviewed to determine toxicity patterns. Adverse events will be summarized and described within each cohort. They will initially be reviewed regardless of attribution, but also whether they are possibly, probably, or definitely related to treatment. In addition, we will review all adverse event data that are graded as 3, 4, or 5 and classified as either “unrelated” or “unlikely to be related” to study treatment in the event of an actual relationship developing. The incidence of severe adverse events or toxicities will be described. We will assess the proportion of patients who experience grade 3 or higher non-hematologic toxicity. To assess tolerability, we will also capture the proportion of patients who go off treatment due to adverse events.

Temporary suspension of enrollment [due to toxicity \(aka stopping rules\) are described elsewhere.](#)

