- g. Adverse events related to vaccination will be assessed on day of vaccination, and 7 days after each Fluzone HD vaccination (in-person visit for significant adverse events). If patient is unable to be seen in-person, every effort will be made to obtain documentation of patient evaluation, treatment, and resolution of vaccine-related toxicities.
- h. Survival information will be collected through chart review only. An in-person clinic visit is not required.

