10.5.2 Evaluation of success of blinding (N/A)

10.5.3 Breaking the study blind / participant code (N/A)

11. ADVERSE EVENTS: LIST AND REPORTING REQUIREMENTS

11.1 Identification of AEs and follow-up

The occurrence of an AE or SAE may come to the attention of study personnel during study visits and interviews of a study participant presenting for medical care, or upon review by a study monitor.

The only adverse events to be captured in this protocol must relate to vaccination or influenza-like illness, and these will be captured on the appropriate CRF. Changes in the severity of these AE's only will be documented to allow an assessment of the duration of the event at each level of severity to be performed. These AEs will be followed to adequate resolution.

Information to be collected includes event description, time of onset, clinician assessment of severity, relationship to study product (assessed only by those with the training and authority to make a diagnosis), and time of resolution/stabilization of the event.

Any medical condition that is present at the time that the participant is screened will be considered as baseline and not reported as an AE. Unanticipated problems will be recorded in the data collection system throughout the study.

The site PI will record all reportable events with start dates occurring any time after patient receives the any study drug until 7 (for non-serious AEs) or 14 days (for SAEs) after the last day of study participation. At each study visit, the investigator will inquire about the occurrence of AE/SAEs since the last visit. Events will be followed for outcome information until resolution or stabilization.

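### Section 10.4.2 promises to review grade 3–5 events judged unrelated to treatment, but the capture rule admits only events related to vaccination or influenza-like illness

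*Combined protocol and SAP*

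**What the plan says.** On analysis, section 10.4.2 says of adverse events: "They will initially be reviewed regardless of attribution". It then promises a second look: "we will review all adverse event data that are graded as 3, 4, or 5" and classed as unrelated or unlikely related, in case a relationship emerges later. The same section will report the proportion of patients with grade 3 or higher non-hematologic toxicity.

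On collection, section 11.1 states: "The only adverse events to be captured in this protocol must relate to vaccination or influenza-like illness". Sections 11.4 and 11.7 repeat this, and 11.4 defines serious events inside it. Footnote g of the schedule in 6.5 is similarly narrow: "Adverse events related to vaccination will be assessed on day of vaccination, and 7 days after each Fluzone HD vaccination". Section 10.4.2 itself says: "All vaccine-related AEs will be recorded with start dates occurring any time after patient receives any study drug".

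Three places read more broadly:
- Section 10.4.2 says that if a participant's "condition deteriorates at any time during the study, it will be recorded as an AE", with no condition on relatedness.
- Section 11.6 asks for all serious events to be reported, also without that condition.
- Footnote b describes the contact at weeks 5, 9, 17 and 21 in both arms: "Involves contact between study personnel and the patient regarding influenza-like illness and SAEs".

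**The concern.** A review of severe events called unrelated is a safeguard against wrong attribution. It works only if those events are on file. Here relatedness is a condition for entering the database, so the safeguard sees only what has already passed the judgment it is meant to check.

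That judgment is not masked. The blinding items in 10.5 are marked not applicable, and the control arm has no injection at weeks 9 and 17. Whoever decides whether an event relates to vaccination can know the arm and whether a dose has just been given.

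At stake is what the safety rates can be said to show. Section 3.5 hopes the trial will change practice, so readers will look to these rates for the tolerability of three doses. They would take the grade 3 or higher proportion as all such events unless told otherwise.

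**Working it through.** The documents give no figure on this point, so the check is to follow each kind of grade 3–5 event through the sections.

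**Step 1. Which events reach the review?**

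| Grade 3–5 event | Captured under 11.1, 11.4, 11.7? | In the planned review of unrelated events? |
|---|---|---|
| A. Attributed to vaccine and remains so | Yes | No, it is reported as related |
| B. Suspected of being vaccine-related, later graded unlikely or not related | Yes | Yes |
| C. Influenza-like illness, graded unlikely or not related to vaccine | Yes, through the second limb of the rule | Yes |
| D. Put down to another cause, such as myeloma or its treatment | No, it meets neither limb | No |

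B and C exist because 11.3 grades causality on every event collected, using a scale that includes the unlikely and not-related categories. Section 10.4.2 promises B, C and D; section 11 delivers B and C.

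**Step 2. Does the broader wording bring D back in?** Not reliably. The deterioration sentence in 10.4.2 would admit some D events, but it conflicts with the recording sentence in the same section and with 11.1. The SAE wording in 11.6 and footnote b has no relatedness condition, but 11.4 defines an SAE within the restriction. Staff following section 11 and staff following the broader sentences would record different events.

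**Step 3. Effect on the reported proportion.** For an arm with N treated patients:

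- proportion reported = (patients with at least one grade 3 or higher non-hematologic event of type A, B or C) / N
- proportion a reader would assume = (patients with at least one such event of type A, B, C or D) / N

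The first cannot exceed the second. The gap is the share of patients whose only such events are type D. No rate is given from which to estimate it.

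**Step 4. Which existing contacts are even between arms?** The row for recording adverse events is marked at three visits in the experimental arm (weeks 1, 9 and 17) and one in the control arm (week 1). Post-dose windows therefore number 3 against 1 per patient, a ratio of 3. The influenza-like-illness and SAE contacts number 4 in each arm (weeks 5, 9, 17 and 21).

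**Step 5. Patients already enrolled under the present rule.** The front page and 10.3 give 50 patients in 2019–2020 and 125 in 2020–2021. 50 / (50 + 125) = 50 / 175 = 28.6% of planned consented patients fall in the first season.

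**The case against.** The strongest reply is that the restriction is stated three times and looks deliberate, and that little rests on the review. Toxicity is summarised descriptively. Section 10.4.6 says toxicity proportions will not be compared between cohorts, 10.4.4 plans no interim analysis, and the stopping rule in 5.5 turns on deaths at least possibly related to therapy. Deaths are also found through the survival follow-up in 5.3. All of this stands, and it limits the seriousness of the point: the primary endpoint is untouched. It does not remove the conflict. Narrow capture is a legitimate choice, but 10.4.2 must then describe what narrow capture can support.

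A reader might infer that the review will have no data at all. The documents do not support that: types B and C are collected, and the broader sentences may bring in others.

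A reader might also infer that the plan biases a between-arm test of harm. It does not plan one. The narrower point is that each arm's descriptive rate is conditional on an unmasked judgment.

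Nor do the documents show that all-cause collection is required. It is one of two ways to make the sections agree.

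A further objection concerns the remedy. All-cause recording only from vaccination day to day 7 after each dose would give the experimental arm three times the observation, raising its count of background events even if the vaccine does nothing. This objection is sound and shapes the fix.

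**Conclusion.** The inconsistency is real and should be corrected. As written, the review described in 10.4.2 cannot be done: it would cover essentially only influenza-like-illness events and vaccine-suspected events later graded down. Severe events put down to other causes would be missing, and the grade 3 or higher non-hematologic proportion would depend on an unmasked attribution that the plan does not disclose.

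The size cannot be stated from the documents, since no rate of unrelated grade 3–5 events is given. The direction is known: against a count of all such events, the reported proportion can only be equal or lower.

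The conclusion assumes that the wording in 11.1, 11.4 and 11.7 is applied as a condition of entry, and that no other form collects severe events of any cause as adverse events.

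**What to change.** Reconcile footnote g in 6.5 and sections 10.4.2, 11.1, 11.4, 11.6 and 11.7 in one of two ways.

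**(a) Widen capture.** Record grade 3–5 events and SAEs regardless of attribution, with attribution as a data field. Cover the same period in both arms, using the existing week 5, 9, 17 and 21 contacts rather than only the post-dose windows. State the period in calendar terms: 11.6 runs to 14 days after the last dose, which, if study drug means Fluzone HD, ends much earlier in the control arm. Report first-season patients, collected under the present rule, separately. The cost is modest extra data entry with no new visits, plus a difference in capture between seasons.

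**(b) Narrow the claim.** Limit the two sentences in 10.4.2 on review regardless of attribution and on unrelated events to captured events, and resolve the deterioration sentence there and the SAE wording in 11.6 to match. Label the safety rates *events judged related to vaccination or influenza-like illness only*. The cost is wording only; the safeguard against misattribution is then limited to the events captured.
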